The total number of EMA surveys for the participant to complete during the Treatment Monitoring Period will vary depending on the schedule of the sessions. While we aim to have sessions twice a week for four consecutive weeks, this may not be the case if there is a holiday which the UW is closed or a session needs to be rescheduled for a variety of reasons. Participants will continue to complete EMAs daily during the entire Treatment Monitoring Period, regardless of the scheduling of sessions.

Finally, the 4-Week Post-Treatment Monitoring Period begins the day after Session 8 and extends for four weeks. The 4-Week Post-Treatment EMA survey asks the same questions as the Baseline EMA survey described above minus the items on treatment credibility and expectancies but with the addition of time spent practicing skills items. There will be a total of 56 EMA surveys for the participant to complete for the 4-Week Post-Treatment Monitoring Period.

Research staff will monitor the EMA data daily for possible missing responses and employ an internal protocol for contacting the participant regarding missed surveys. This protocol will be strict enough such that participants who are not completing surveys are followed up appropriately, but also allow enough flexibility so that the number of contact attempts is reasonable and will depend on where the participant is in study participation and their unique circumstances. For example, a participant who has withdrawn from treatment due to issues of time commitment but remains intent-to-treat may warrant less frequent contacts about missed surveys compared to someone who remains in treatment and is fully engaged.

If a participant defers to a future cohort after starting the 2-Week Baseline Monitoring Period but before getting randomized, s/he will need to redo the 2-Week Baseline Monitoring Period at the time of the future cohort as we require a minimum 14 days of EMA collection prior to treatment.

Participants will be compensated \$1 for the completion of each EMA survey, plus a \$6 “bonus” for each week they complete ≥ 12 surveys. At the end of each EMA Monitoring Period, the number of EMA surveys completed will be tallied and total payment calculated for the entire period. A single check for the total payment for EMA surveys completed for that period will be sent via USPS mail and accompanied by a payment cover letter.

ActiGraphs

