Research staff will monitor ActiGraph wear compliance through questions on the EMA survey. Specifically, there is a question on the evening EMA asking the participant if s/he wore the device at all times during the past 24 hours. If a participant answers “No”, a follow-up question will ask approximately how long they were not wearing the device. A staff member will employ an internal protocol for contacting the participant regarding ActiGraph non-wear. This protocol will be strict enough such that participants who are not wearing the device are followed up appropriately, but also allow enough flexibility so that the number of contact attempts is reasonable and will depend on where the participant is in study participation and their unique circumstances. For example, a participant who has withdrawn from treatment but remains intent-to-treat AND who has reported difficulties with wearing the ActiGraph may warrant less frequent contacts about non-wear compared to someone who remains in treatment and is fully engaged.

If a participant defers to a future cohort after starting the 2-Week Baseline Monitoring Period but before getting randomized, s/he will need to redo the 2-Week Baseline Monitoring Period at the time of the future cohort (i.e., s/he will need to wear the ActiGraph again).

Participants will be compensated \$70 for the return of the ActiGraph after the 4-Week Post-Treatment Monitoring Period. The check will be sent via USPS mail and accompanied by a payment cover letter.

To encourage wear compliance and the timely return of activity monitors, we will also offer participants the option to receive a summary of their ActiGraph data at study completion (after they have finished the 6-Month Extended Assessment). If the participant desires, we will send them either via USPS postal mail or email a document that may include data on one or more of the following: activity counts, energy expenditure, MET rates, steps taken, physical activity intensity, sleep latency, total sleep time, wake after sleep onset, and/or sleep efficiency. This information will be sent with a cover letter.

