All group treatment sessions will be audio recorded using Zoom's built-in recording function to ensure compliance to treatment procedures. These recordings may also be used for training purposes. A portion of treatment sessions will be randomly selected and reviewed/coded by study researchers to ascertain fidelity to protocol. Study clinicians will receive feedback during regularly scheduled supervision sessions with either Drs. [name], [name], or [name] (depending on treatment condition) and corrective feedback will be provided as needed if they diverge from protocol.

The study clinicians will notify participants before the start of the session that s/he will be recording the session, and all participants in the group must have provided consent to audio record during the informed consent process. Participants who withdraw their consent to record after the groups start but who still want to participate in the study may still complete all remaining study procedures with the exception of treatment sessions.

Audio recordings will only be reviewed by study personnel and used for assessing consistency between study clinicians. The audio recordings will not be labeled with any identifying information. The only identifying information that will be contained within the

recordings will be participants' voices and if the study clinician or if group members state participants' names during the discussion.

Treatment Intervention Discontinuation

A participant will be withdrawn from the treatment intervention if s/he (1) engages in behavior that is disruptive to the group, and/or (2) engages in behavior that interferes with the appropriate administration of the group treatment.

However, participants who are withdrawn from the study treatment intervention will be invited to complete study assessments at post-treatment, 3-month, and 6-month follow-up as well as any remaining EMA surveys and continue to wear the ActiGraph to allow for complete data for the planned intent-to-treat analyses (see below). Participants will receive payment for the time it takes to provide outcome data at each assessment point.

An electronic treatment withdrawal/termination case report form will be completed for participants who withdraw or are terminated from treatment.

Intent-to-Treat (ITT)

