We will monitor session attendance and session dates to track percentage of attendance and to account for absenteeism and reasons for any missed sessions. Reasons for attrition will be assessed for participants who withdraw. Given clinician-rated participant engagement during sessions was associated with dropout in our preliminary research,³⁸ we will assess this at each session for each participant. Enactment of treatment-specific changes will be assessed by homework practice, assessed via EMA. Comparisons between the treatment conditions in dropout rates will be made, and variables shown to differentiate the groups will be included as covariates.

To minimize possible missed EMA data, we will provide financial incentives for completing the EMA surveys (i.e., \$1.00 per assessment, plus a \$6.00 “bonus” for each week they complete ≥ 12 assessments). In addition, a staff member will monitor the EMA data daily for possible missing responses and employ an internal protocol for contacting the participant regarding missed surveys. This protocol will be strict enough such that participants who are not completing surveys are followed up appropriately, but also allow enough flexibility so that the number of contact attempts is reasonable and will depend on where the participant is in study participation and their unique circumstances. For example, a participant who has withdrawn from treatment due to issues of time commitment but remains intent-to-treat may warrant less frequent contacts about missed surveys compared to someone who remains in treatment and is fully engaged.

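### Staff may chase missed diaries, and in some cases device non-wear, less after treatment withdrawal, so intent-to-treat data collection can depend on a post-randomisation event that the missing-data plan does not name

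*Combined protocol and SAP*

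**What the plan says.** On missed diaries, D6j (EMA Surveys) gives this example of flexible follow-up: "a participant who has withdrawn from treatment due to issues of time commitment but remains intent-to-treat may warrant less frequent contacts about missed surveys". D6n repeats it in a paragraph whose stated purpose is to reduce missed diary data.

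On the device, D6j (ActiGraphs) and D6n give a narrower example. It concerns someone "withdrawn from treatment but remains intent-to-treat AND who has reported difficulties with wearing the ActiGraph may warrant less frequent contacts about non-wear", so both conditions must hold.

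Behind both examples is a general rule. An internal protocol must be strict enough to secure appropriate follow-up, yet "allow enough flexibility so that the number of contact attempts is reasonable and will depend on where the participant is in study participation", together with individual circumstances. That internal protocol is not part of the documents, and no minimum number of attempts is stated.

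D6m (Treatment Intervention Discontinuation) invites people withdrawn from treatment to complete the later assessments "as well as any remaining EMA surveys and continue to wear the ActiGraph to allow for complete data for the planned intent-to-treat analyses". The Intent-to-Treat paragraph of D6m makes the same offer to anyone randomised who cannot attend or who chooses to leave treatment.

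D6t plans a variable-by-variable check of whether fully observed variables predict missingness, FIML under missing at random, and selection or pattern-mixture models with multiple imputation if missingness is not ignorable. F4d calls for a discussion among investigators if EMA adherence falls below 80%.

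**The concern.** Leaving treatment happens after randomisation. It is plausibly related to how a participant is responding, and its frequency may differ between arms. If reminder effort falls when someone leaves, the amount of data collected depends on that event, among the very people whom D6m follows in order to complete the intent-to-treat data.

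The diary supplies the primary outcome (pain interference) and two of the three primary mechanisms (catastrophizing and non-judgment). The third, activity, comes from the device, but "Research staff will monitor ActiGraph wear compliance through questions on the EMA survey". An evening diary that is missed and not pursued therefore also hides non-wear while it could still be corrected.

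The exposed quantities are the late-treatment slopes (Days 29-42) used in the *b* paths and the Aim 1 endpoint (Days 43-46). The early slopes (Days 15-28), on which the *a* paths rest, are exposed through people who leave early.

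**Working it through.** **1. The plan's own figure.** D5 inflates 240 completers for 20% drop-out: 240 / (1 - 0.20) = 300, which reproduces the stated enrolment. This allows for loss from the study. It says nothing about people who stop treatment, stay in the study and return fewer diaries, and no other figure in the documents covers them.

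**2. The two parts side by side.** D6m wants complete diary and device data after withdrawal from treatment. D6j and D6n allow less pursuit of those data for some of the same people. The second does not forbid the first, but it permits unequal effort by treatment status.

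**3. Would participants be lost, or data thinned?** D6s needs two ratings per epoch for a slope, and D6t averages a morning and an evening slope, each from up to 14 ratings in a 14-day epoch. As an assumption, let a withdrawer complete 43% (half of the 86% diary rate that section C reports for a completer sample), with independent misses. The chance of fewer than two ratings in one stream is 0.57^14 + 14 × 0.43 × 0.57^13 = 0.0004 + 0.0040 = 0.0044, about 0.4%. So under scattered misses almost every withdrawer still contributes a slope. The likelier effect is thinner data. Complete absence would require the person to stop answering altogether.

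**4. What thinner data do to a slope.** Assume one rating a day, independent errors and time scaled 0 to 1 over 14 days. All 14 days give a sum of squares of 14 × (14² - 1) / 12 / 13² = 227.5 / 169 = 1.346. The first two days alone give 2 × (1/26)² = 1/338. The standard-error ratio is √(1.346 × 338) = 21.3. With only the first and last days the sum of squares is 0.5, and the ratio is √(1.346 / 0.5) = 1.64. Both patterns meet the two-rating minimum. The carry-forward rule in D6t would fill the gap in the first pattern and pull its slope towards zero.

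**5. Exposure of the endpoint.** Days 43-46 at two diaries a day give at most 4 × 2 = 8 surveys, all after treatment has ended.

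**6. Would the adherence trigger notice?** Let *w* be the share withdrawn from treatment (assumed; the documents give none), and let those who stay complete 86%. Pooled adherence is (1 - *w*) × 0.86 + *w* × *c*, where *c* is completion among withdrawers. Setting this to 0.80 gives *c* = (0.80 - (1 - *w*) × 0.86) / *w*:

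- *w* = 10%: (0.80 - 0.774) / 0.10 = 26%
- *w* = 20%: (0.80 - 0.688) / 0.20 = 56%
- *w* = 30%: (0.80 - 0.602) / 0.30 = 66%

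Completion among withdrawers could fall to these levels before the pooled figure reached the trigger. This shows what an unsplit trigger can miss. It does not predict completion.

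**7. The missingness check.** Attendance is recorded at every session and treatment withdrawal has its own case report form (D6m), so both are available. D6t names neither. A non-significant check leads to treating the data as randomly missing, although such a test cannot detect dependence on unobserved values.

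**The case against.** The examples are permissive and narrow. The diary example concerns people who left for lack of time; the device example also requires reported wear difficulty. Both sit within a protocol that must secure appropriate follow-up. Nothing in the documents takes away the automated twice-daily alerts or the payments from people who leave treatment; only extra staff contacts may be fewer. All of this stands.

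A reader might infer that withdrawers will have the most missing data by design. The documents do not support that: the stated aim is complete data, and no completion rate after withdrawal is given. A reader might also infer a definite inflation of average improvement, or a definite shrinkage of arm differences, by assuming that halved diary completion removes half the withdrawers and that withdrawers do not improve. That does not follow either. Two ratings suffice for a slope (step 3), the lack of improvement would be invented, and an arm difference in late pain interference is not among the six planned tests. Nor can it be said that the unequal effort goes unrecorded, since the internal protocol is not available to read.

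D6t does have a non-ignorable route, D6n compares drop-out between arms and adjusts for variables that differ, and missingness that depends on recorded withdrawal can be handled as missing at random once withdrawal is in the model. That also stands; the gap is that D6t does not say withdrawal will be there.

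Finally, pressing people who left for lack of time could push them out of the study and cost the 3- and 6-month data. That risk is real, but an option to ask for fewer contacts largely meets it.

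**Conclusion.** The point holds in a limited form. The protocol permits staff effort on missed diaries, and on non-wear when wear difficulty was also reported, to depend on treatment withdrawal, for people whom D6m follows to complete the intent-to-treat data. The risk is sparser, carried-forward or missing late-treatment and Day 43-46 data in withdrawers. The missingness check does not name withdrawal or attendance, and the 80% trigger could miss a shortfall confined to withdrawers.

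No size or direction of bias can be given. The documents state neither a treatment-withdrawal rate nor a completion rate afterwards. Carrying scores forward can pull a slope towards no change, while losing withdrawers' data altogether would leave the estimate to those who stayed, so even the sign is open. Steps 3, 4 and 6 rest on the stated assumptions and show mechanisms only. This is a cheap improvement, not a flaw that undermines the primary analysis.

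**What to change.** - **D6j and D6n:** replace the examples with one contact trigger and one maximum number of attempts for all randomised participants in each monitoring period, whatever their treatment status, for both missed EMAs and ActiGraph non-wear. Reduce contact only when the participant asks, and log the request with its date.
- **D6t:** add session attendance and treatment withdrawal to the missingness check, and include them as auxiliary variables in FIML. FIML helps only where a slope is missing; slopes built on carried values are not, which is why equal collection effort comes first.
- **Reporting:** give EMA and wear completion by arm and treatment status.

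The cost is a wording change, an edit to the internal contact protocol, and somewhat more contacts by existing staff. Withdrawers bear some added burden, with a small risk of prompting full withdrawal from the study, which the option to request fewer contacts limits.

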In addition to these primary recruitment sources, we will also recruit using social media, online forums, websites, patient advisory networks, and other online mediums that are pertinent to chronic pain. We will also encourage providers, participants, and interested individuals to pass along our study information to others as they see fit.

The recruitment sources described above will provide participants who are representative of the general population with a history of chronic pain and enhance the generalizability of the study results.

D5. Participants

We propose to enroll 300 participants in order to ensure complete data from 240 randomized participants, assuming a very conservative 20% drop-out rate (the dropout rate in our other studies has never reached below 15%). We will monitor the dropout rate on an ongoing basis, and modify the number of participants recruited as needed to ensure a final sample of N = 240 study completers.

Eligibility Criteria

Inclusion Criteria:

- (1) Age \geq 18 years;
- (2) Endorse having low back pain as a primary or secondary pain problem in the past 6 months;
- (3) Meet criteria for having a chronic pain problem (\geq 3 months, with pain experienced on \geq 50% of days in past 6 months);
- (4) Average intensity of chronic pain \geq 3 on a 10-point scale for most days of the previous 3 months;
- (5) Chronic pain interference for general activities \geq 3 on a 10-point scale for the past 3 months;
- (6) Able to read, speak, and understand English;
- (7) If currently taking analgesic or psychotropic medication, medications must have been stabilized for \geq 4 weeks prior to this study; and
- (8) Availability of a telephone, webcam, and microphone through computer or telephone, as well as daily internet access.

Exclusion Criteria:

- (1) Primary pain condition is headache;
- (2) Severe cognitive impairment;
- (3) Current alcohol or substance dependence;
- (4) Active malignancy (e.g., cancer not in remission), terminal illnesses, or serious medical conditions that may interfere with either study participation or with receiving potential treatment benefits (e.g., severe lupus);
- (5) Inability to walk (defined as unable to walk at least 50 yards), which would limit the ability of participants to benefit from the activation skills intervention;
- (6) Significant pain from a recent surgery or injury;
- (7) Pain condition for which surgery has been recommended and is planned;

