Participants who do not return their ActiGraphs within a reasonable amount of time will be contacted by research staff via phone, email, text, and/or letter to encourage the participant to send the device back as soon as possible. We will only have a limited number of devices on hand and need the devices back promptly to ensure we can 1) collect the stored data and 2) have enough devices ready to deploy for the next return point/next cohort of participants.

D6k. Randomization

We will begin randomizing participants no sooner than six days after the start of the 2-Week Baseline Monitoring Period and continue to randomize until the day before the first treatment group starts. All participants in the current cohort will be reviewed to see if they completed all required baseline procedures and are thus eligible for randomization. The required baseline procedures are as follows:

1. Provided Baseline data and Demographics;
2. Completed Pre-Treatment Assessment;
3. Participated in technology training session and verbally agreed they are comfortable with all study software and with participating in group sessions using the videoconferencing software;
4. Completed re-assessments of pain interference and frequency/consistency;

5. Completed at least 7/14 EMA surveys during Week 1 of the Baseline Monitoring Period.

All participants need to complete the above required baseline procedures before they will be randomized; however, exceptions to meeting all randomization criteria may be given by researchers on a case-by-case basis should there be any extenuating circumstances that prevent the participant from meeting all randomization criteria. For example, a participant could have trouble accessing or completing EMAs not due to lack of participant effort. Participants who do not meet the EMA completion criterion above may be offered the opportunity to be contacted in the future should the criterion be revised. At that point, they would be re-screened for eligibility and will re-complete any Baseline procedures that are needed. If the Baseline procedures are completed the subsequent time around, then the participant will be eligible for randomization.

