For all participants who are randomized to receive one of the three study treatments but are unable to participate in that cohort's treatment sessions, the participant will always be asked to complete study assessments for that cohort and included in study analysis unless they withdraw their participation from the study. This means that, post-randomization, if a participant is unable to attend the treatment s/he was assigned to OR decides to withdraw from treatment, s/he will be offered the opportunity to continue with EMAs, wear the activity monitor, and complete extended assessments for that cohort in which randomization had occurred. The participant will not be allowed to defer to another cohort to participate in treatment. Once a participant is randomized, s/he cannot be deferred to a later treatment cohort, even if they do not participate in a single session of the cohort they are randomized in. If a participant needs to defer to another cohort, this is only allowed **before** they have been randomized.

D6n. Study Design Enhancements: Treatment Fidelity, Missed Sessions and EMA Assessments, Participant Engagement, and Study Retention Strategies

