Because it is likely that we will encounter at least some missing data despite procedural efforts by research staff to minimize its occurrence, we have attempted to further address missing data in a number of ways via our data analysis approach. First, we will examine potential patterns of missing data that represent confounds contributing to biased slopes. So, for each participant, analyses to identify potential patterns in missing data will be conducted to determine if they are “ignorable” (see Schafer & Grahem, 2002)¹⁰⁷. If >5% of the participants do not provide adequate data, the sample will be divided into two groups (missing data, no missing data) and fully observed variables will be examined to determine if they significantly predict missingness on the affected outcome. This test will be done on a variable-by-variable basis. If this analysis is non-significant, the missingness will be considered “observed at random” and the procedures described below for calculation of slope coefficients in the instance of missing data will be used, without necessitating the use of multiple imputation procedures. However, if no data is available to calculate slope via the below methods, in Mplus, the missing data (slopes and estimated end values from slopes) are treated automatically (by default) by estimating the full model from available data using full information maximum likelihood (FIML). The Mplus robust maximum likelihood (MLR) estimator using FIML permits missing completely at random (MCAR) and missing at random (MAR), and MLR uses SEs that are corrected for non-normality and also uses a corrected chi-square fit statistic. If data missingness is not ignorable, Heckman’s selectivity models of pattern-mixture models with multiple imputation will be used to model the “missingness” for each participant before calculation of slopes from the daily EMA and ActiGraph data.

There are several ways to treat data that are deemed to be missing at random (from the daily EMA and ActiGraph data) using the slope method. For example, consider the six cases below (from real data). The dependent variable was measured at five equally spaced intervals within the epoch. Within the current study, there are additionally two observations per day, and we propose to calculate the slopes from morning and evening observations, and to average those slopes.

Cases	0	0.25	0.5	0.75	1	Slope	Difference
1	12	14	15	15	10	-1.2	-2
2	12	10	11	10	7	-4	-5
3	23	19	13	13	12	-11.2	-11

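### The Intent-to-Treat rule in D6m, read literally, excludes randomised participants who withdraw from the study, which conflicts with the intent-to-treat label and with the missing-data plan in D6t

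*Combined protocol and SAP*

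**What the plan says.** - **Inclusion rule.** The Intent-to-Treat paragraph of D6m concerns people who are randomised "but are unable to participate in that cohort's treatment sessions". They are to be asked for that cohort's assessments and "included in study analysis unless they withdraw their participation from the study".
- **Extension to treatment withdrawal.** The next sentence adds those who decide to leave treatment: "s/he will be offered the opportunity to continue with EMAs, wear the activity monitor, and complete extended assessments". Deferral to a later cohort after randomisation is ruled out.
- **Stated principle.** Under Treatment Intervention Discontinuation, D6m explains that continued assessment is sought "to allow for complete data for the planned intent-to-treat analyses".
- **Intent-to-treat as a status.** D6j and D6n give the example of "a participant who has withdrawn from treatment due to issues of time commitment but remains intent-to-treat", wording that treats intent-to-treat as something a person can keep or lose.
- **Missing data.** D6t calculates slopes from incomplete series, carries the closest score to the ends of an epoch, and otherwise relies on "estimating the full model from available data using full information maximum likelihood (FIML"). It makes no exception for people who have left the study.
- **Data held at randomisation.** D6k requires the Pre-Treatment Assessment and "Completed at least 7/14 EMA surveys during Week 1 of the Baseline Monitoring Period", with case-by-case exceptions.
- **Planned losses.** D5 plans 300 enrolled for 240 with complete data, "assuming a very conservative 20% drop-out rate".

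**The concern.** An intent-to-treat set is fixed by randomisation. Here membership depends on a later choice by the participant, and that choice may be related to the assigned arm and to early response. D6n itself notes that clinician-rated engagement was associated with dropout in the team's preliminary work, so leaving may well be informative.

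The comparison at risk is the effect of treatment condition on the early mechanism slope (paths a1 and a2 in D6s, Step 2). That test helps to decide between the Shared and the Specific Mechanisms Models. Its outcome is measured in days 15-28, so someone who leaves the study in week 3 or 4 of treatment has already supplied it for the diary mechanisms. Excluding that person discards an observed outcome. It also lets the analyst choose between D6m and D6t after dropout is known.

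**Working it through.** **1. Which data exist at study withdrawal.**

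| Time of leaving the study | Baseline diaries | Early-treatment diary slope (days 15-28) |
|---|---|---|
| After randomisation, before Session 1 | Yes, apart from D6k exceptions | None |
| During days 15-28 | Yes | Often: D6s needs only two ratings per epoch |
| After day 28 | Yes | Normally yes |

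Diary entries go through a web portal, are monitored daily and are downloaded regularly (D6j, D6r), so they are in hand. Activity counts differ: they stay on the device until it is returned (D6r), so the third mechanism is available only for leavers who send it back.

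**2. The two sections applied to one person.** Take someone who leaves the study on day 32. Under D6t, the early slope is used and the late slope is estimated around or treated as missing. Under a literal reading of D6m, the person is not in the analysis. A missing-data method acts only on people in the analysis set, and nothing says which section prevails.

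**3. The plan's own figure.** 240 / (1 - 0.20) = 300, which reproduces D5. The drop-out allowance is 300 - 240 = 60. The documents do not split it into loss before randomisation, incomplete data and study withdrawal, so the number excluded by the clause lies between 0 and 60. No stated sample size is wrong because of this point.

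**4. Bias in an arm contrast.** Let p be the proportion of an arm that is excluded and d the gap, in SD of the early slope, between stayers and withdrawers. The arm mean equals (1 - p) x (stayer mean) + p x (withdrawer mean), so the stayers' mean is too favourable by p x d. With the same d in two arms, the contrast is biased by (p2 - p1) x d. All rates below are assumptions.

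| Withdrawal, two arms | d = 0.25 | d = 0.5 | d = 1.0 |
|---|---|---|---|
| 20% v 20% | 0 | 0 | 0 |
| 15% v 25% | 0.025 | 0.05 | 0.10 |
| 10% v 30% | 0.05 | 0.10 | 0.20 |

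**5. Check with a logistic withdrawal model.** Assume a standard-normal early slope, no true arm difference, withdrawal after day 28 of 10%, 20% and 30% in the three arms, and log-odds of leaving lower by 0.5 or 1.0 per SD of early improvement. Numerical integration gives these shifts in the stayers' means:

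- 0.5 per SD: 0.05, 0.10 and 0.14 SD; contrast between the 10% and 30% arms 0.09 SD.
- 1.0 per SD: 0.09, 0.17 and 0.25 SD; contrast 0.16 SD.

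These agree with step 4. If the observed early slopes are kept, the bias in this contrast is zero, because in this scenario everyone has one.

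**6. What that does to the test.** With 240 analysed (90, 80 and 70 per arm), the spurious arm effect is eta-squared 0.0015 (0.5 per SD) or 0.0048 (1.0 per SD). The chance of a false three-arm difference at alpha 0.05 becomes about 8% or 15%.

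**The case against.** Several points on the other side stand.

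- **Scope.** The sentence expressly covers people unable to attend, and the next adds treatment withdrawers. It says nothing direct about someone who attends and later leaves the study. Applying the same exception to that person is natural, but it is an inference.
- **No deletion is stated.** A reader might infer that the protocol orders data already collected to be removed for every study withdrawer. It does not say so. The clause can also be read as meaning only that no further assessments are sought, and D6t taken alone would keep the partial data.
- **Consent text.** The information statement may say what happens to data collected before withdrawal, and it is not in the text available for review.
- **Size.** A reader might also infer that a false Specific Mechanisms finding is likely. The documents give no withdrawal rate by arm. Even the assumed 10/20/30% split gives an effect below the 0.01 eta-squared that D6s treats as small. D6s also requires a significant b path and post hoc tests that link each treatment to its own target.
- **Mitigation.** D6n compares dropout between arms and adjusts for variables that differ.

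These points limit the claim but do not remove it. The clause is the only text that says who is in the intent-to-treat analysis, and the wording in D6j and D6n fits its literal sense. D6t does not say that it overrides the clause, and covariate adjustment does not bring excluded people back.

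**Conclusion.** The point holds as an unresolved conflict. D6m makes inclusion depend on not withdrawing from the study, while the intent-to-treat label and D6t imply that everyone randomised stays in, with whatever data they gave. If the clause is followed, the a1/a2 comparison is among those who remained in the study.

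The effect on the results cannot be derived from the documents. From 0 to 60 people could be affected. The bias in the arm contrast is zero when withdrawal rates and selection are equal across arms. It is about 0.1-0.2 SD under an assumed 10% v 30% withdrawal with withdrawers 0.5-1.0 SD worse than stayers, and smaller under milder assumptions. For activity counts, the point applies only where the device comes back.

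This should be fixed before analysis because it defines the primary analysis population. It does not invalidate the design or the sample size.

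**What to change.** Replace the clause in D6m with wording such as:

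> All randomised participants are analysed in the arm assigned. Data collected up to study withdrawal are included unless the participant asks for their removal, subject to the information statement. Later values are handled as missing under D6t.

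Add a cross-reference in D6t so that the two sections agree, and report the number of study withdrawals by arm and by epoch (before Session 1, days 15-28, days 29-42, post-treatment).

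The cost is one replaced sentence, one cross-reference, one descriptive table and a check that the information statement allows data already collected to be kept. It needs no new data, participants or change in sample size.
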